6.1. Dosimetry

All patients will receive stereotactic body radiation therapy (SBRT) for a total dose of 50 Gy with 12.5 Gy/fraction in 4 fractions or 60 Gy in 10 fractions prescribed to the planning target volume (PTV). It is recommended that prescribed isodose line cover more than 95% of the PTV if normal tissue dose is within threshold (as defined in 6.5). In the event that normal tissue dose is considered unacceptably high when treated with 50 Gy in 4 fractions, then patients can be alternatively treated with 60 Gy in 10 fractions. For lesion close to critical structures, compromised PTV coverage is allowed in order to meet normal tissue dose constraints. In this case, treating physician should make clinical judgments regarding optimal target coverage and normal tissues sparing.

There is no or little aperture margin recommended. The external border of the PTV will be covered by a lower isodose surface than usually used in conventional radiotherapy planning, which typically ranges from 70-95%. However, higher isodoses (hotspots) must be manipulated to occur within the target and not in adjacent normal tissue. Heterogeneity correction should be applied for planning. The recommended radiation dose and fraction will be either at the initial XRT dose (50 Gy in 4 fractions or 60 Gy in 10 fractions) lower dose may be used if felt to be clinically indicated by the treating physician. Other tumor sites may be treated for palliation concurrently or sequentially if needed at the discretion of the treating radiation oncologist.

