All patients who achieve systemic benefit (based on physician discretion) but later progress will be given the option of receiving reinduction. Optional radiation can be administered during reinduction. If administered, radiation will be given similar to what was done in the initial treatment. After the first round of reinduction, patients may receive additional reinduction if during their most recent post cycle 4 imaging disease control is observed without severe (grade >3) toxicity. Patients with either liver or lung lesions amenable to SBRT (either 50 Gy in 4 fractions or 60 Gy in 10 fraction) will be enrolled on this trial.

Treatment group 1) Ipilimumab + BMS-986156 (30 mg / 100 mg) x 4 for safety assessment (No SBRT) → Nivolumab x 26

Treatment group 2) Sequential (late SBRT) Ipilimumab + BMS-986156 (dose as determined in group 1) x 2 → SBRT → Ipilimumab + BMS-986156 (dose as determined in group 1) x 2 → Nivolumab x 26

Treatment group 3) Concurrent (early SBRT) Nivolumab (480 mg Q4W) + BMS-986156 (30mg) + SBRT → Nivolumab + BMS-986156 x 3 (30mg) → Nivolumab x 22

Group 1, 20 patients: Ipilimumab + BMS-986156 (30 or 100 mg) Dose Escalation → Nivolumab x 26 (up to 2 year maintenance)

Day 1 and every 21 days: Ipilimumab therapy at 3 mg/kg as a 90 minute intravenous (IV) dose and BMS-986156 at either 30 mg or 100 mg dose as a 60 min IV dose will be given in an outpatient setting. Dose cycles will be repeated every 21 days: on days 1, 22, 43, and 64 for a total of 4 cycles. Maintenance therapy of Nivolumab (480mg Q4W) will start day 85 and continue every 28 days, for 26 cycles.

A modified 3+3 dose escalation then expansion to a total of 10 patients per arm (escalation + expansion, if applicable) will be performed on two dose levels of this combination therapy. Details on de-escalation are presented under section 7.7.1.

Group 1

[figure not shown]

Diagram of Treatment Schedule for Ipilimumab + BMS-986156 (30 or 100 mg) Dose Escalation → Nivolumab x 26 (Treatment Group 1)

Group 2, 20 patients: Ipilimumab + BMS-986156 x 2 → SBRT → Ipilimumab + BMS-986156 x 2 → Nivolumab x 26 (up to 2 year maintenance)

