Day 1 and every 21 days: Ipilimumab therapy at 3 mg/kg as a 90 minute intravenous (IV) dose and BMS-986156 (dose as determined in group 1) as a 60 min IV will be given in an outpatient setting. Dose cycles will be repeated every 21 days: on days 1, 22, 43, and 64 for a total of 4 cycles. Nivolumab (480 mg Q4W) will start day 85 and continue every 28 days for 26 cycles. Enrollment of this group will start based on the following criteria. If 2 out of 6 patients, or less, display DLTs, then, enrollment of group 2 can begin. Alternatively, if 3 out of 6 patients, or more, display DLTs, then, enrollment of group 2 cannot begin until 10 patients have been treated in group 1.

SBRT: SBRT will be given after 2 doses of ipilimumab and BMS-986156 on days 29-32 for 50 Gy in 4 fractions or on days 29-40 for 60 Gy in 10 fractions (no SBRT during weekends): SBRT will be directed at 1-4 targetable liver or lung lesion(s). To minimize treatment breaks, patients may start radiation on a Monday.

Group 2

[figure not shown]

Diagram of Treatment Schedule for Ipilimumab + BMS-986156 x 2 → SBRT → Ipilimumab + BMS-986156 x 2 → Nivolumab x 26 (Treatment group 2).

Group 3, 20 patients: Nivolumab + BMS-986156 x 1 + SBRT → Nivolumab + BMS-986156 x 3 → Nivolumab x 22

First dose of Nivolumab + BMS-986156 and SBRT will be given concurrently (early) and followed by Nivolumab + BMS-986156 x 3; then, Nivolumab monotherapy for 22 cycles. Nivolumab will be administered for a total of 26 cycles, either as a combination or monotherapy, in this group. Enrollment of patients for this group will start around the same time as group 1. Choice of treatment group will be at the discretion of PI and treating physician.

Nivolumab therapy at 480 mg dose will be given on day 1 as a 30 minute IV dose and BMS-986156 at 30 mg dose will be given on day 1, 29, 57, 85 as a 60 min IV in an outpatient setting. Nivolumab monotherapy will start on day 113 and will continue for 22 cycles.

SBRT: SBRT will be given on days 1-4 (days 2-5 are acceptable if scheduling does not permit radiation to begin same day as infusions) for 50 Gy in 4 fractions or on days 1-12 for 60 Gy in 10 fractions (no SBRT during weekends). SBRT will be directed at 1-4 targetable liver or lung lesion(s). To minimize treatment breaks, patients may start radiation on a Monday.

Group 3

[figure not shown]

Diagram of Treatment Schedule for Nivolumab + BMS-986156 x 1 + SBRT → Nivolumab + BMS-986156 x 3 → Nivolumab x 22 (Treatment group 3)

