4.1. Inclusion Criteria

1. Patients must have histological confirmation of solid metastatic cancer (all groups) with at least one metastatic or primary lesion in the liver or lung/chest (groups 2 and 3). All Groups must have measurable disease per irRC criteria.
2. Patients who have completed prior systemic anti-cancer therapies, an interval of 5 drug half-lives or 4-weeks whichever is shorter, is required, prior to enrollment on study. Note: patients with anaplastic thyroid will be waived from this inclusion criteria given the rapid trajectory of their disease.
 - Patients that have previously progressed on immunotherapy such as ipilimumab, anti-PD-1, anti-PDL-1 or talimogene laherparepvec (T-VEC) will be eligible.
3. All patients must have at least one metastatic or primary lesion within the lung/chest or liver located in an anatomical location amenable to SBRT treatment with 50 Gy in 4 fractions or with 60 Gy in 10 fractions, except for group 1.
4. Repeat radiation in fields previously radiated will be allowed at the discretion of the treating physician.
5. Age ≥ 18 years
6. ECOG performance status ≤ 2 (Karnofsky $>60\%$).
7. Patients must have normal organ and marrow function as defined below: (use of growth factors or blood transfusion to achieve these requirements is not allowed 2 weeks prior to study enrollment)
 - Total bilirubin ≤ 2.0 mg/dL. (Does NOT apply to patients with Gilbert's Syndrome)
 - AST(SGOT)/ALT(SGPT) $<2.5 \times$ institutional upper limit of normal.
 - WBC $\geq 2500/\mu\text{L}$, ANC $\geq 1000/\mu\text{L}$
 - Platelets $\geq 75\text{K}$
 - Hemoglobin $\geq 9\text{g/dL}$
 - Creatinine $\leq 2.0 \times \text{ULN}$
8. Patients must be willing and able to review, understand, and provide written consent before starting therapy.
9. Patients with brain metastasis will be included as long as they are free of neurologic symptoms related to metastatic brain lesions and who do not require or receive systemic corticosteroid therapy, $> 10 \text{ mg/day}$ in the 14 days prior to beginning the trial ($\leq 10 \text{ mg steroid}$, e.g.: prednisone, is allowed). We will allow patients with stable brain metastases (clinically and radiographically) for ≥ 4 weeks to enroll on the protocol.

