 - If 1 of 3 subjects have a DLT in dose level, 3 more patients will then be enrolled at this dose level. If only 1 of the 6 total subjects at dose level has a DLT, then this dose level will be considered safe and all other patient in this arm will be treated at this dose level.
 - If 2 of 6 subject has DLT then the dose will be de-escalated as per table below.
 - If 2 of 3 subjects have a DLT at dose level 1, then the dose will be de-escalated as per table below

Dose De-Escalation of BMS-986156 when combining with Nivolumab plus SBRT.

Dose Level 1	480mg Nivolumab + 30 mg BMS-986156
---------------------	------------------------------------

Dose Level -1 480mg Nivolumab + 10 mg BMS-986156**7.1.2. Reinduction for all arms**

Reinduction will be allowed for patients in which the treating physician feels there was benefit from the trial treatment. It will consist of repeating the original treatment using the same schedule for each arm. Radiation may be given during reinduction, but is not required. Pending the treating radiation oncologist judgment, additional radiation therapy to a previously non-irradiated lesion can be administered during re-induction. Timing of radiation during reinduction will be at the discretion of treating Radiation Oncologist.

The target lesion for radiation will be chosen by the treating radiation oncologist. The target lesion must not have been previously irradiated. The target lesion does not have to be within the same organ that was initially treated during the initial treatment (e.g. patients who received initial lung lesion irradiation can have liver or a bone lesion irradiated during re-induction). Radiation dose and fraction will be either at the initial dose (50 Gy in 4 fractions or 60 Gy in 10 fractions) or at a lower palliation dose (30 Gy in 10 fractions) and may also be combined with low dose radiation ranging from 200cGy-1000cGy in multiple fractions, at the discretion of the treating radiation oncologist.

Other tumor sites may be treated for palliation concurrently or sequentially if needed at the discretion of the treating radiation oncologist.

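### A lower SBRT dose is not limited to re-induction, and a DLT-free patient given less than the tested SBRT can fill one of the six places that clear a group 2 or 3 level

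*Combined protocol and SAP*

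**What the plan says.** **Radiation dose.** After prescribing 50 Gy/4 or 60 Gy/10, Section 6.1 continues: "The recommended radiation dose and fraction will be either at the initial XRT dose", names the two schedules again, and adds "lower dose may be used if felt to be clinically indicated by the treating physician". Re-induction is not mentioned. Elsewhere the first course is only 50 or 60 Gy:

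- Section 1: "lesions amenable to SBRT (either 50 Gy in 4 fractions or 60 Gy in 10 fraction" and, for group 2, "on days 29-32 for 50 Gy in 4 fractions or on days 29-40 for 60 Gy in 10 fractions"; group 3 has the same two schedules from day 1.
- Section 6.3: a prescription of 50 or 60 Gy to the PTV.
- Section 12: footnote 4 of the group 2 calendar and footnote 4 of the group 3 calendar.

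Inclusion criterion 3 (Section 4.1) requires a lesion "amenable to SBRT treatment with 50 Gy in 4 fractions or with 60 Gy in 10 fractions, except for group 1"; this governs suitability, not the dose delivered.

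Section 6.5 twice mentions a corresponding dose de-escalation that is defined nowhere. The de-escalation tables in 7.1.1.2 and 7.1.1.3 lower drug doses only.

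**Who counts.** Sections 7.1.1.2 and 7.1.1.3 call a level safe when one of six subjects has a DLT and de-escalate at two of three or two of six. Sections 10.1 and 10.2.1 make a patient evaluable for toxicity on any study drug. Their stricter rule, for toxicity and response together, asks for one or two drug treatments plus half of the planned radiation. The opening of Section 10 sends a summary to the IND Office after every three evaluable patients per group, without saying what SBRT dose makes a patient evaluable.

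**The concern.** Four of the five primary objectives (Section 2.1) concern the safety of a drug regimen given with SBRT. Six patients decide whether a group 2 or 3 level is safe. If one of them received less than the tested SBRT and had no DLT, that patient still supports the declaration that the full combination is safe.

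This can arise in two ways. A physician may prescribe less, relying on 6.1. Or a patient may be prescribed 50 or 60 Gy and receive only part of it, or none; the any-drug rule admits that patient too. If less radiation means fewer DLTs, the decision tilts toward safe.

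**Working it through.** **1. Do the counting rules exclude such a patient?** No.

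- Any-drug rule: no radiation condition.
- Half-of-planned rule: a patient planned and treated at a reduced dose completes 100% of the plan. Even if planned means the protocol dose, 30 Gy in 10 fractions (the palliative dose named in 7.1.2) is 30/50 = 60% or 30/60 = 50% of it, so the patient still qualifies.
- Cohort summaries in Section 10: no SBRT-dose criterion.
- Section 7.3.5 withdraws patients who refuse or do not comply with SBRT. It does not say they leave the six or are replaced, and it does not cover a reduction chosen by the physician.

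**2. How much could one such patient matter?** The plan gives no operating characteristics for the six-patient rule. I take clearing as one or fewer DLTs in six; stopping early at two of three does not change that probability. Let p be the DLT rate at full dose and q the rate in the one under-dosed patient. The documents give no DLT rate by SBRT dose, so p = 1/3 (two of six is the result that triggers de-escalation) and all values of q are assumptions. p = 6% is the DLT rate that Section 3.3 reports for ipilimumab plus SBRT without BMS-986156.

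Six full-dose patients: (1−p)^6 + 6p(1−p)^5.

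- p = 1/3: 0.0878 + 0.2634 = 0.351
- p = 0.06: 0.6899 + 0.2642 = 0.954

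Five full-dose patients plus one at q: (1−q)·A + q·B, where A = (1−p)^5 + 5p(1−p)^4 and B = (1−p)^5. For p = 1/3, A = 0.4609 and B = 0.1317.

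| q (p = 1/3) | Chance of clearing |
|---|---|
| 0.40 | 0.329 |
| 1/3 | 0.351 |
| 0.15 | 0.412 |
| 0.10 | 0.428 |
| 0 | 0.461 |

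The largest rise is 0.461 − 0.351 = 0.110. For p = 0.06 and q = 0, clearing is 0.968, a rise of 0.014.

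**3. A narrower estimate.** Section 7.5 cites toxicity after SBRT of 2% (liver, grade 3 or higher) and 7.9% (lung). Suppose under-dosing removes exactly that much from p = 1/3. Clearing then rises by (A − B) times the reduction: 0.329 × 0.02 = 0.7 points to 0.329 × 0.079 = 2.6 points. These rates are not for SBRT with these drugs, and the same section notes higher toxicity by lesion location.

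**4. More than one such patient.** At p = 33% and q = 10%, clearing goes from 0.358 with none to 0.434, 0.521 and 0.616 with one, two and three.

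**5. Time for a radiation effect to appear.** Group 2: SBRT ends on day 32 or 40 and the DLT window closes on day 43, leaving 43 − 40 = 3 to 43 − 32 = 11 days. Group 3: 29 − 12 = 17 to 29 − 4 = 25 days.

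**The case against.** The strongest reply is that the lower-dose sentence is re-induction text in the wrong place. An initial dose makes sense only relative to a later course. Section 7.1.2 opens its dose sentence almost identically, "Radiation dose and fraction will be either at the initial dose", and both sections contain "Other tumor sites may be treated for palliation concurrently or sequentially if needed at the discretion of the treating radiation oncologist". The protocol also has its own sequence when a plan fails constraints: 50 Gy/4, then 60 Gy/10, then reduced PTV coverage (7.1) or ineligibility subject to physician judgement (6.5). None of these is a lower prescription. This probably describes the intent, but 6.1 does not say so, and the reference to dose de-escalation in 6.5 points the other way.

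A second reply is that half of the planned radiation naturally means half of 50 or 60 Gy, a floor of 25 to 30 Gy. Even so, a half-dose patient counts, and the any-drug rule has no floor.

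Third, the IND Office reviews every three evaluable patients and must approve dose-level changes. The decision is therefore not an unreviewed tally. The review could catch such a case, but no written criterion requires it to.

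A reader might infer that the plan biases the safety decision toward safe, or that 11 points is the expected error. The documents support neither. They do not say how often a lower dose would be used. The direction can reverse if lower doses go to higher-risk patients, for example under inclusion criterion 4: "Repeat radiation in fields previously radiated will be allowed at the discretion of the treating physician". The ceiling requires under-dosing to remove every DLT, drug-related ones included. Section 7.2.1 says that only DLTs of the irradiated organ define the MTD in groups 2 and 3, then lists many systemic events; if those count, the effect shrinks.

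**Conclusion.** The concern holds as a minor one. The conflict between 6.1 and the other first-course dose statements is plain from the text, as is the absence of any rule keeping an under-dosed, DLT-free patient out of the six. The consequence is less certain. With one such patient the chance of clearing rises by at most 11 points at an assumed rate of 1/3 and by at most 1.4 points at 6%. It falls by about 2 points (0.351 to 0.329) if that patient's own rate is 40%. Several such patients would matter more, but nothing in the documents suggests that number. Any effect is probably smaller in group 2, where few days remain after SBRT before the DLT window closes.

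**What to change.** 1. In 6.1, limit the lower-dose sentence to re-induction under 7.1.2. In 6.5, delete both references to a corresponding dose de-escalation. Leave the existing sequence (50 Gy/4, then 60 Gy/10, then reduced PTV coverage or ineligibility) unchanged.
2. In 7.1.1.2, 7.1.1.3 and 10.1, and for the evaluable patients in the opening of Section 10, state for groups 2 and 3:
   - a DLT-free patient fills one of the six places only if first-course 50 Gy/4 or 60 Gy/10 was both prescribed and delivered, with reduced PTV coverage allowed and recorded;
   - a DLT in any treated patient counts and fills a place;
   - other DLT-free patients are replaced from within the planned 20 and stay in the general toxicity tables.

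Testing delivery as well as prescription matters: otherwise a patient prescribed 50 Gy who received little or none of it would still fill a place.

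**Cost.** Protocol wording, with no patients beyond 20 per group. The decision may wait for another patient. The rule is slightly conservative, because an under-dosed patient can add a DLT but not a clear. With one such patient, clearing is (1−q)·P6 + q·(1−p)^5, where P6 is the value for six full-dose patients. At p = 0.10, P6 = 0.886 and (1−p)^5 = 0.590, giving 0.871 for q = 0.05 and 0.856 for q = 0.10: a fall from 89% to 86–87%. At p = 0.06 it falls from 95% to 94% (0.943 for q = 0.05, 0.941 for q = 0.06).

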6.2. Radiation Technique

Patients will be evaluated for regularity of breathing, responsiveness to feedback guidance, breath-hold capability. Based on this evaluation, a treatment delivery technique will be selected among the following:

1. Breath-hold (with or without feedback guidance).
2. Gated treatment.
3. Free-breathing (with or without feedback guidance).
4. Abdominal compression.
5. A combination of the above techniques.

A CT scan obtained using the same method of respiratory management as intended for treatment will be required for treatment planning purposes. This CT simulation may include a 4-dimensional CT (4DCT) for free-breathing, gated or abdominal compression techniques or repeated breath-hold CTs for breath hold techniques. Feedback guidance, including visual and/or audio techniques, will be used for all patients who would both benefit from and respond to training with such devices.

4DCT is a fast CT scan that capable of imaging tumor position during the entire breath cycle. A CT scan is obtained with the patient in each couch position for a whole breath cycle (usually lasting 5 to 6 seconds in each position) followed by repositioning to the next couch position. Following a scan, the computer resorts all images and reconstructs the tumor positions for an entire breath cycle, i.e., a movie file is created which captures organ movement throughout the breath cycle. Radiotherapy will be designed based on the path of organ motion captured by 4DCT.

6.3. Target Volumes

1. Gross Target Volume (GTV): Gross tumor as observed on a non-contrast CT should be delineated on lung (for lung tumors) or abdominal (for liver tumors) windows from either 4DCT or repeated breath-hold CTs (see IGTV below).

2. Internal Gross Target Volume (IGTV): IGTV is the volume containing the GTV throughout its motion during respiration or positional variability during repeated breath holds. The motion during free breathing (with or without abdominal compression) will be determined from 4DCT, the variability of tumor location during breath hold will be determined by repeated breath hold CTs obtained on the same day. One method to combine the data from the multiple CT datasets is to create a maximal intensity projection (MIP) that is used as an aid to contour the IGTV. All CT datasets will be transferred to the treatment planning system for reference.

3. Clinical Target Volume (CTV) + Planning Target Volume (PTV): GTV plus 5-10 mm margin (based on physician discretion). Due to tight PTV margin, CTV margin is not recommended to be edited except when normal tissue toxicity is concerning based on treating physician's judgment. The prescribed dose of radiation (either 50 Gy or 60 Gy) will be dosed to the PTV, we recommend 95% coverage if possible, lower coverage is allowed if clinically indicated.

6.4. Daily treatment setup:

The appropriate immobilization will be chosen for each patient. Most patients will be immobilized with arms up using a commercially available vacuum immobilization bag that extends from the patient's head to their pelvis combined with a wing board.

On-board imaging: Daily on-board imaging such as CT on-rails, cone beam CT, or 4-D cone beam CT will be conducted prior to each radiation fraction. Position adjustment and target coverage confirmation will be performed daily based on imaging study. The setup uncertainty will be kept to less than a 3 mm (2 s) variation. This value is based on the uncertainties of the couch readouts added in quadrature with $\frac{1}{2}$ the voxel size of the CT. Adjustment of patient position is needed if target coverage is judged by the treating physician to be inadequate and/or critical normal tissues toxicity is concerning. Repeated on-board CT after position adjustment is recommended if more than 5 mm shift is conducted.

6.5. Dose Volume Constraints

Maximum doses allowed in radiation planning are as outlined below. In the event that a treatment plan cannot reasonably meet dose constraints for 50 Gy in 4 fractions (or the corresponding dose de-escalation), then a separate plan will be generated for 60 Gy in 10 fractions. In the event that the subsequent treatment plan cannot reasonably meet dose constraints for 60 Gy in 10 fractions (or the corresponding dose de-escalation), then this patient is ineligible for this study, pending treating physician judgement.

50 Gy in 4 fractions dose constraints:

- Spinal Cord: 25 Gy \leq 1 cc
- Lung: V20 \leq 20%, V10 $<$ 30%, V5 $<$ 40%
- Esophagus: 40 Gy \leq 1 cc, 36 Gy \leq 10 cc
- Trachea: 40 Gy \leq 1 cc, 36 Gy \leq 10 cc
- Main bronchus and bronchial tree: 48 Gy \leq 1 cc, 40 Gy \leq 10 cc
- Heart: 48 Gy \leq 1 cc, 40 Gy \leq 10 cc
- Brachial plexus: 40 Gy \leq 1 cc, 35 Gy \leq 10 cc
- Major vessels: 48 Gy \leq 1 cc, 40 Gy \leq 10 cc
- Skin (defined as outer 0.5 cm of body surface): 40 Gy \leq 1 cc, 35 Gy \leq 10 cc
- Kidney: 8.4Gy to 200cc

60 Gy in 10 fractions dose constraints:

- Spinal Cord: 40 Gy \leq 1 cc
- Lung: V20 \leq 20%, V10 $<$ 30%, V5 $<$ 50%
- Esophagus: 60 Gy \leq 1 cc, 40 Gy \leq 10 cc
- Trachea: 70 Gy \leq 1 cc, 60 Gy \leq 10 cc
- Main bronchus: 70 Gy \leq 1 cc, 60 Gy \leq 10 cc
- Heart: 70 Gy \leq 5 cc, 50 Gy \leq 10 cc
- Brachial plexus: 50 Gy \leq 1 cc, 40 Gy \leq 10 cc
- Major vessels: 70 Gy \leq 5 cc, 60 Gy \leq 10 cc

- Skin (defined as outer 0.5 cm of body surface): $60 \text{ Gy} \leq 1 \text{ cc}$, $50 \text{ Gy} \leq 10 \text{ cc}$
- Kidney: $V50 \leq 33\%$

For patients who have received previous radiotherapy, the attending radiation oncologist is required to evaluate the previous treatment plan, particularly the dose delivered to critical structures and make a clinical judgment based on BED, previous radiation therapy, and current SBRT doses using above dose volume constraints as a guide.

7. Treatment Plan

Notice: Treatment schedules shall have a standing window of allowance of +/- 3 days unless patient/logistical/medical reasons intervene. Any treatment day that falls on a weekend or holiday will be scheduled on the next business day. Patients will undergo a therapy wash out period of 5 drug half-lives or 4-weeks whichever is shorter. We will allow prior radiation to other sites with no washout period prior to study entry as long as the high dose regions of the prior and proposed radiation fields do not overlap. If patient had prior radiation with an overlap in the intended radiation field and prior there must be a washout period of three months.

Any treatment day that falls on a weekend or holiday will be scheduled on the next business day. For treatment or dose modification questions, please contact [name] by [contact]) or email ([contact]), Thoracic Radiation Oncology, or [name] by [contact]) or e-mail ([contact]), Clinic Center for Targeted Therapy (CCTT). No investigational or commercial agents or therapies other than those described below may be administered with the intent to treat the patient's malignancy.

Initially, patients that are enrolled on study will be placed in either treatment group 1 or in treatment group 3. After BMS-986156 dose determination in group 1, enrollment of patients in group 2 will be initiated.

